APPENDIX 3 COMMONLY USED CORTICOSTEROID EQUIVALENTS

Medication	Dose Equivalence
Prednisone	20 mg
Cortisone	100 mg
Hydrocortisone	80 mg
Prednisolone	20 mg
Methylprednisolone	16 mg
Triamcinolone	16 mg
Budesonide	4 mg
Dexamethasone	3 mg
Bethamethasone	2.4 mg

APPENDIX 4 MEDICATION WASHOUT PERIODS

WASHOUT TIMES OF MEDICATIONS BASED ON 5 HALF-LIVES

Medication	Discontinuing Prior to Signing Consent
Abatacept (CTLA4Ig)	24 weeks
Alefacept	12 weeks
AMG 623 (blisibimod)	24 weeks
Anifrolumab	12 weeks
Atacicept (TACI-Ig)	12 weeks
Belimumab	24 weeks
Cyclophosphamide	24 weeks
Cyclosporine (except for CSA eye drops)	4 weeks
Danazol	4 weeks
Dapsone	4 weeks
Eculizumab	12 weeks
Efalizumab	12 weeks
Epratuzumab	24 weeks
Intravenous globulin	4 weeks
Leflunomide	8 weeks (4 weeks for washout with cholestyramine)
Lenalidomide with cholestiramine	8 weeks
Lupuzor	12 weeks
Memantine	4 weeks
Natalizumab	24 weeks
Ocrelizumab	48 weeks (or 24 weeks with recovery of B cell)
Pimecrolimus	4 weeks
Plasmapheresis	24 weeks
Retinoids (oral or topical)	4 weeks
Rituximab	48 weeks (or 24 weeks with recovery of B cell)
Sirolimus	4 weeks
Tacrolimus	4 weeks
Thalidomide	8 weeks
Tocilizumab	12 weeks

APPENDIX 5 BILAG-2004 (STUDY-SPECIFIC MODIFIED CRITERIA)

CCI

[REDACTED]

APPENDIX 6 INJECTION SITE REACTION GRADING SCALE

Adverse event Injection site reaction	Grade 1	Grade 2	Grade 3	Grade 4	Grade 5
Definition: A disorder characterized by an intense adverse reaction (usually immunologic) developing at the site of an injection	Tenderness with or without associated symptoms (eg, warmth, erythema, itching)	Pain; Lipodystrophy; Edema; phlebitis	Ulceration or necrosis; Severe tissue damage; Operative intervention indicated	Life-threatening consequences; urgent intervention indicated	Death
Pain	Mild pain	Moderate pain; limiting instrumental ADL	Severe pain; limiting self-care ADL	-	-
Rash maculopapular/Erythema/Induration Definition: A disorder characterized by the presence of macules (flat) and papules (elevated). Also known as morbilliform rash, it is one of the most common cutaneous adverse events, frequently affecting the upper trunk, spreading centripetally, and associated with pruritus.	Macules/papules covering <10% BSA with or without symptoms (eg, pruritus, burning, tightness) Erythema covering <10% BSA with or without symptoms (eg, pruritus, burning, tightness)	Macules/papules covering 10% - 30% BSA with or without symptoms (eg, pruritus, burning, tightness); limiting instrumental ADL; Erythema 30% BSA with or without symptoms (eg, pruritus, burning, tightness); limiting instrumental ADL	Macules/papules covering > 30% BSA with or without associated symptoms; limiting self-care ADL Erythema covering > 30% BSA with or without associated symptoms; limiting self-careADL	-	-

ADL = active daily living

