6.2.2.6 Adverse Events of Special Interest

AEs of special interest in this study include the following:

1. Anaphylaxis and serious allergic reactions
2. Grades 2 to 5 injection site reaction, including erythema, pain, and induration (See [APPENDIX 6](#))
3. Drug Induced Liver Injury (DILI) assessed following Hy's Law
4. Malignancy
5. Opportunistic infections such as disseminated histoplasmosis, cryptococcosis, and disseminated tuberculosis
6. Cryptosporidiasis

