6.2.2.6.1 Anaphylaxis and Serious Allergic Reactions

Anaphylaxis will be defined according to the National Institute of Allergy and Infectious Diseases/Food Allergy and Anaphylaxis Network (NIAID/FAAN) criteria.⁴² In the event of anaphylactic reaction or severe/serious hypersensitivity/allergic reaction, the patient must discontinue IP and emergency resuscitation measures implemented. In case of other mild to moderate hypersensitivity reaction, depending on the severity, the investigator may manage in accordance with the standard-of-care.

Anaphylaxis is highly likely when any one of the following 3 criteria is fulfilled:

1. Acute onset of an illness (minutes to several hours) with involvement of the skin, mucosal tissue, or both (eg, generalized hives, pruritus, or flushing, swollen lips-tongue-uvula) and at least 1 of the following:
 - a. Respiratory compromise (eg, dyspnea, wheeze-bronchospasm, stridor, reduced peak expiratory flow [PEF], hypoxemia)
 - b. Reduced blood pressure or associated symptoms of end-organ dysfunction (eg, hypotonia [collapse], syncope, incontinence)

2. Two or more of the following that occur rapidly after exposure to a likely allergen for that patient (minutes to several hours):
 - a. Involvement of the skin-mucosal tissue (eg, generalized hives, itch-flush, swollen lips-tongue-uvula)
 - b. Respiratory compromise (eg, dyspnea, wheeze-bronchospasm, stridor, reduced PEF, hypoxemia)
 - c. Reduced blood pressure or associated symptoms (eg, hypotonia [collapse], syncope, incontinence)
 - d. Persistent gastrointestinal symptoms (eg, crampy abdominal pain, vomiting)
3. Reduced blood pressure after exposure to known allergen for that patient (minutes to several hours):
 - a. Systolic blood pressure of less than 90 mm Hg or greater than 30% decrease from the patient's baseline

6.2.2.6.2 *Injection Site Reactions*

Injection site reactions are to be captured and reported as AEs. These will include Grades 2 to 5 injection site erythema, pain, and induration (see [APPENDIX 6](#)). The investigator should provide a clear description of the observed or reported AE including location and severity. All concomitant treatments used to treat injection site reactions should be recorded and captured in the eCRF, together with the AE of injection site reactions.

6.2.2.6.3 *Potential Drug-Induced Liver Injury*

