6.2.7 Injection Site Reactions

Patients will be monitored for local injection site reactions as specified in the Schedule of Assessments (Section 3.4). Local injection site reactions will be assessed at 2 hours postdose at baseline, and predose for each injection after baseline. Injection site reactions should be managed according to the standard of care. Injection site reactions, Grades 2 to 5, are to be reported as AEs of special interest (see [Section 6.2.2.7.3](#)).

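### Appendix 6 cannot properly grade the injection-site erythema, induration and mild pain that the protocol names as Grade 2 to 5 events of special interest

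*Protocol*

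**What the plan says.** Three places in the protocol set the threshold. Section 6.2.2.6 lists as special interest "Grades 2 to 5 injection site reaction, including erythema, pain, and induration". Section 6.2.2.6.2 says of the reactions to be reported: "These will include Grades 2 to 5 injection site erythema, pain, and induration". Both point to Appendix 6. Section 6.2.7 repeats the cut: "Injection site reactions, Grades 2 to 5, are to be reported as AEs of special interest". Section 6.2.2.7.3 requires such events to be reported immediately or within 24 hours.

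Appendix 6 has three rows:

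- **General injection site reaction.** Tenderness, with erythema as a possible associated symptom, is Grade 1. Grade 2 reads "Pain; Lipodystrophy; Edema; phlebitis". Ulceration, necrosis and severe tissue damage are Grade 3.
- **Pain.** Mild is Grade 1, moderate is Grade 2 and severe is Grade 3.
- **Maculopapular rash, erythema and induration together.** The definition is that of a widespread rash. Grade 1 is "Erythema covering <10% BSA with or without symptoms". Grade 2 gives "Macules/papules covering 10% - 30% BSA with or without symptoms" for the rash but "Erythema 30% BSA with or without symptoms" for erythema. Grade 3 is anything above 30%.

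The Pain row and the rash row have no Grade 4 or 5.

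**The concern.** The step from Grade 1 to Grade 2 decides whether an injection site reaction is a special-interest event with expedited reporting. If the table cannot place a named finding on one side of that step, the count does not measure what Sections 6.2.2.6 and 6.2.2.6.2 say it measures. There are four difficulties:

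- a whole-body scale is applied to a local lesion;
- one named finding, induration, has no criterion;
- the printed erythema grades leave a gap;
- two rows disagree about mild pain.

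Injection site reactions are a listed safety endpoint in both phases, according to the objectives and endpoints tables reproduced in Appendix 7. In Phase 1b, safety and tolerability inform the choice of dose. A special-interest rate that hardly registers isolated erythema, and that depends on which row a site uses for mild pain, is a weak basis for comparing doses or arms.

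**Working it through.** The protocol states no figure to reproduce. The check is geometry for erythema and a side-by-side reading for the rest.

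**Erythema.** The Appendix 6 inputs are Grade 1 below 10% BSA and Grade 2 printed as 30%. Adult BSA is not given, so it is assumed to be 1.5 to 2.0 m² (15,000 to 20,000 cm²), with 1.4 to 2.2 m² as a wider check.

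- Threshold area = fraction × BSA. Equivalent circle diameter = 2 × √(area / π).
- At 10%: 0.10 × 15,000 = 1,500 cm², diameter 2 × √(1,500 / π) = 43.7 cm. 0.10 × 20,000 = 2,000 cm², diameter 50.5 cm.
- At 30%, as printed for Grade 2: 4,500 to 6,000 cm², diameter 75.7 to 87.4 cm.
- A patch 10 cm across: π × 10² / 4 = 78.5 cm². 78.5 / 15,000 = 0.52% and 78.5 / 20,000 = 0.39%. The 10% threshold is therefore 1,500 / 78.5 = 19 to 2,000 / 78.5 = 25 times the area of that patch.
- Wider range, 1.4 to 2.2 m²: the 10% threshold is a circle 42.2 to 52.9 cm across. A 10 cm patch is 0.36 to 0.56%. A 20 cm patch (314.2 cm²) is 1.4 to 2.2%.

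Every local lesion in this range is Grade 1 on area, and the result does not depend on where in the assumed range BSA lies. The general row offers no other route for erythema alone, because there it is only an associated symptom at Grade 1.

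**Induration.** The word occurs in the heading of the rash row. The cells of that row speak only of macules, papules and erythema, and the general row does not list induration. No grade can be read off for it.

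**Grade gap.** In the Grade 2 cell, rash runs from 10% to 30%, while erythema is given as 30% alone. With Grade 1 below 10% and Grade 3 above 30%, erythema from 10% to under 30% has no grade as printed.

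**Pain.** The general row puts pain of unspecified intensity at Grade 2. The Pain row puts mild pain at Grade 1. The same event is thus of special interest on one row and not on the other, and nothing in the appendix says which row governs.

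**The case against.** The best defence has four parts.

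- **Nothing is lost from the safety data.** Section 6.2.2.6.2 has injection site reactions captured and reported as adverse events, with location and severity, and the safety endpoint itself carries no Grade 2 limit. This stands. A reader might infer that local erythema disappears from the safety record, but the documents do not support that. Only the special-interest subset and the assigned grade are affected.
- **Reactions of substance still reach Grade 2.** Erythema accompanied by pain, edema, lipodystrophy or phlebitis can qualify by the general row, and tissue damage is Grade 3. This also stands, and it confines the erythema point to isolated lesions. The functional-limitation wording in the rash row might be read as another route to Grade 2, but the semicolon before it does not say whether it means and or or. Leaving isolated mild redness below the threshold could be a deliberate choice. However, the protocol names erythema as a special-interest finding, and the table does not separate mild from marked local redness.
- **The dedicated Pain row is the natural one for isolated mild pain**, since the general row is defined as an intense reaction. That is a reasonable reading, but it is not written down, and sites may differ.
- **The 30% cell looks like a slip or a lost symbol.** That cannot be excluded. Reading it as 10% to 30% closes the gap but leaves the threshold at 44 to 50 cm.

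A reader of "predose for each injection after baseline" in Section 6.2.7 might also infer that, after the first dose, sites look for reactions only a month after each injection. The documents do not support that as a finding. Section 6.2.7 defers to the Schedule of Assessments, whose current version is not in the part at hand. The replacement Phase 1b extract in Appendix 7 keeps a Day 7 check. Nor is a mismatch between the change log's stated reason and the current text an error in the plan.

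**Conclusion.** The point holds for classification. Applied exactly as written, Appendix 6 gives isolated injection-site erythema Grade 1 unless it spans roughly 44 to 50 cm, gives induration no grade, and gives mild pain either of two grades. Those are the three findings that Sections 6.2.2.6 and 6.2.2.6.2 name. The special-interest count would understate isolated erythema, could not classify induration consistently, and could vary by site for mild pain.

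The diameters rest on an assumed BSA of 1.5 to 2.0 m² and a circular lesion, and the conclusion is unchanged from 1.4 to 2.2 m². The size of any under-count cannot be given, because the protocol gives no expected reaction rates. The general capture of adverse events and the primary efficacy analysis are not affected. The table should be corrected, but the problem does not threaten the trial's main conclusion.

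**What to change.** In Appendix 6:

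1. Replace the BSA-based row with criteria for the local site, set separately for erythema and for induration, so that each named finding has a grade.
2. If any BSA wording is kept, correct the Grade 2 erythema cell or reconcile it with the range printed for macules and papules, so that no interval is left ungraded.
3. State one row that governs pain, so that mild pain has a single grade.

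Moving erythema and induration to the general injection site reaction row would not solve the problem: erythema there is only a Grade 1 associated symptom, and induration is not listed.

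The cost is one table and matching site guidance. Somewhat more events may be reported as special interest.

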APPENDIX 7 PROTOCOL SUMMARY OF CHANGES

The protocol summary of changes was moved to the end of the protocol for easier readability.

Significant changes are described in the table below. Changed text is displayed for the first major occurrence only. Deleted text is presented in strikethrough format, and added text is presented in bold format.

Section	Description of Changes	Rationale
Global	Add: Added ' Protocol Date and Version: 21 March 2018; V3.0 ' to the header.	Administrative
Global	Change: Changed Version number from V2.0 (Amendment 1) to V3.0 (Amendment 2) and Version date from 14 November 2017 to 21 March 2018 .	Administrative
Global	Change: Changed subjects to patients .	Replaced 'subjects' to 'patients' since the enrolled participants are with SLE condition
Global	Made administrative and editorial (formatting, typographical, and grammatical) updates.	Administrative
PROTOCOL SUMMARY, Background and Rationale	Add: The Phase 2 portion will be a proof of concept (POC) study, where dose selection will be based on the data monitoring committee (DMC) and sponsor's assessment of safety, tolerability, immunogenicity, and PK and PD data from the MAD study of 30 patients treated with BOS161721/placebo	Clarification that POC dose selection will be based on DMC and sponsor assessment
PROTOCOL SUMMARY, Objectives and Endpoints	The objectives and endpoints sections were combined together and are now represented in a table format in order to demonstrate which endpoints correspond to each objective. Only primary and secondary objectives and endpoints are listed within the synopsis. Additional edits were made to some objectives and endpoints. Some new endpoints were added to the study. An exploratory objective, to examine PK and PD effects of BOS161721 in subjects with mild to moderate SLE, was changed to 'secondary objective'. Changes to the objectives and endpoints are noted below: MAD Phase 1b Study	Updated for clarity and to provide a comprehensive list of endpoints identified in the protocol

Section	Description of Changes	Rationale
OBJECTIVES	ENDPOINTS	
Primary		

 To assess safety, tolerability, and immunogenicity of repeat doses of BOS161721 (20, 60, and 120 mg) administered SC in adult patients with moderately to severely active SLE on limited background standard of care treatment, in order to estimate the optimal dose. 	
Safety Endpoints
 
 Incidence and severity of adverse events (AEs) and serious adverse events (SAEs), related AEs, AEs leading to study drug discontinuation, AEs by severity and relatedness Injection site reactions Columbia Suicide severity Rating Scale (C-SSRS) 12-lead electrocardiograms (ECGs) parameter results at each visit and change from baseline Vital signs (blood pressure [BP], heart rate, and temperature) parameter results at each visit and change from baseline Clinical laboratory results and change from baseline Physical examinations changes from baseline Anti-drug antibodies (ADAs) Study drug exposure/compliance Concomitant medication usage 	
Secondary		

 To characterize the PK of BOS161721 and select the optimal dose of BOS161721 based on safety, PK, and PD effects in patients with mild to moderate SLE. 	
Pharmacokinetic Endpoints
 
 BOS161721 concentration by visit and time point Maximum observed concentration (C_{max}), first time to maximum concentration (T_{max}), area under the concentration-time curve (AUC), $t_{1/2}$, systematic clearance (C_L), volume of distribution (V_d) 
Pharmacodynamic Endpoints
 
 Results and changes (or shifts) from baseline to each visit in phosphorylated signal transducer and activator of transcription 3 (pSTAT3), C3 and C4 levels, and leukocyte immunophenotype Results and changes (or shifts) from baseline in anti-double-stranded DNA (dsDNA), antinuclear antibodies (ANA), anti-Sjögren syndrome A and B 	

Section	Description of Changes	Rationale
	(SSA, SSB), Smith (Sm), and antiphospholipid (APL) autoantibodies at each visit 
 • Results and changes (or shifts) from baseline in abrogation of IL-21 gene signature at each indicated visit 	
Exploratory		

 • CCI [REDACTED] 	
 • CCI [REDACTED] • CCI [REDACTED] 	
The rules for CS usage during the trial, as well as limitations of other prohibited medications, are applied on the analytical end to ensure SRI-4 responders meet all necessary criteria.

Section	Description of Changes	Rationale
		
CCI
 
[Redacted]

 CCI [Redacted] 		
 CCI [Redacted]

 CCI [Redacted] 		
 CCI [Redacted]

POC Phase 2 Study

OBJECTIVES	ENDPOINTS
Primary	

 To demonstrate a superior effect of BOS161721 at the chosen dose compared with placebo for response on the SLE Responder Index 4 (SRI-4) 	
Primary Efficacy Endpoint
 
 The proportion of subjects with a SRI-4 response at Day 210 (see Section 6.3.4.1)
Secondary	

Section	Description of Changes	Rationale
	
To demonstrate a superior effect of BOS161721 at the chosen dose compared with placebo for response on clinical indicators of SLE activity, in adult patients with moderately to severely active SLE on limited background standard of care treatment
	
Secondary Efficacy Endpoints
 
 • The proportion of subjects with: 
 - SRI-4 response at each visit - SRI-5 and SRI-6 response (Section 6.3.4.2) - a sustained reduction of oral corticosteroid (CS) (≤ 10 mg/day and \leq Day 0 dose) between Day 120 and Day 210 - new BILAG A flare or > 1 BILAG B flares relative to baseline through Day 210 - PGA worsening - a BICLA response - a CLASI response - medication failures • Results and changes from baseline in: 
 - CLASI - swollen and tender joints ACR-28 - SLEDAI-2K - SLICC/ACR damage index • Time to medication failure • Duration of SRI-4 response • Time to first SRI-4 response • Time to BILAG A flare or > 1 BILAG B flare compared to baseline through Day 210
	
Safety
 
 • To assess safety and tolerability of repeat doses of BOS161721 (20, 60, and 120 mg) administered SC in adult patients with moderately to severely active SLE on limited background standard of care treatment 	
Safety Endpoints
 
 • Incidence and severity of adverse events (AEs) and serious adverse events (SAEs), related AEs, AEs leading to study drug discontinuation, AEs by severity and relatedness • Injection site reactions • C-SSRS • 12-lead ECGs parameter results at each visit and change from baseline • Vital signs (blood

Section	Description of Changes	Rationale
		pressure [BP], heart rate, and temperature) parameter results at each visit and change from baseline 
 • Clinical laboratory results and change from baseline • Physical examinations changes from baseline • ADAs • Study drug exposure/compliance • Concomitant medication usage
	Exploratory	

 • CCI [REDACTED] 	
 • CCI [REDACTED] 	
 • CCI [REDACTED]

 • CCI [REDACTED] 	
 • CCI [REDACTED] 	
 • CCI [REDACTED]

 • CCI [REDACTED] 	
 • CCI [REDACTED] 	
 • CCI [REDACTED]

Section	Description of Changes	Rationale
PROTOCOL SUMMARY , Study Design	Replace: The trial will consist of a staggered MAD Phase 1b and POC Phase 2 studies. Both studies will be double blinded with each patient having the same number of doses (7), and visits; the duration will be 180 days, followed by a 90-day follow-up safety observation period. With: The trial will consist of 2 double-blinded studies : MAD Phase 1b and POC Phase 2. Patients may receive a total of 7 SC monthly doses of study drug on Days 0, 30, 60, 90, 120, 150, and 180, followed by safety follow-up visits at Days 210, 240, and 270.	Clarification that patients will not have the same number of visits in both studies.
PROTOCOL SUMMARY , Study Design Section 1.2.4 , Risk-Benefit Assessment	Delete: Two weeks after the last patient in Cohort 3 receives the second dose, the DMC and Boston Pharmaceuticals will conduct a data review for the first interim analysis (IA1). At that time, a decision will be made to suggest which dose should be carried forward into the POC Phase 2 study.	The futility analysis was removed due to the modest size of the trial but more importantly because the least reliable data (high placebo response) is known to occur during the first half of the study (before week 24) when futility analysis was planned
PROTOCOL SUMMARY , Study Design Section 3.1.2.2 , POC Study Design	Add: For the POC study, approximately 156 additional patients will be randomized to active or placebo groups in a 2:1 ratio.	Clarification on POC sample size

Section	Description of Changes	Rationale

PROTOCOL SUMMARY, Study Design
	
Replace:
 
Data from 60 patients, including the 12 from the MAD study, or 6 fewer if the low dose is chosen, who are in the cohort of the chosen dose for the POC study who complete 3 months of treatment will be used in a second IA (IA2) at Day 90 to assess if the trial could stop for an early futility conclusion. If futility is not claimed in the IA2, the POC study will continue to approximately 156 patients.
 
Following the 6 month treatment period, primary and secondary efficacy endpoints will be assessed for each patient, after providing their Day 180 disease activity assessments. DMC monitoring will be conducted periodically throughout the study as described in the DMC charter.
 
With:
 
DMC safety reviews will be conducted periodically throughout the study as described in the DMC charter.
	
Removed assessment information from section, and the futility analysis was removed due to the modest size of the trial but more importantly because the least reliable data (high placebo response) is known to occur during the first half of the study (before week 24) when FA was planned

PROTOCOL SUMMARY, Main Criteria for Inclusion and Exclusion (inclusion criterion 6, sub-bullet ii)
 
Section 4.4, Inclusion Criteria (inclusion criterion 6, sub-bullet ii)
	
Replace:
 
ii Points from lupus headache and organic brain syndrome are also excluded
 
With:
 
ii Points from lupus headache and organic brain syndrome will also be excluded
	
Corrected to maintain consistency

Section	Description of Changes	Rationale

PROTOCOL SUMMARY, Main Criteria for Inclusion and Exclusion (inclusion criterion 7, sub-bullets a and b)
	
Replace:
 
7 Patients must have at least 1 of the following manifestations of SLE, as defined by the BILAG criteria as modified for use in this study, which must be confirmed by the central data reviewer:
 
 a. BILAG A or B score in the mucocutaneous body system b. BILAG A or B score in the musculoskeletal body system due to active polyarthritis as defined in the protocol Section 4.4. c. If only one “B” and no “A” score is present in the mucocutaneous body system or in the musculoskeletal body system due to arthritis, then at least 1 “B” must be present in the other body systems for a total of 2 “B” BILAG body system scores 
With:
 
7 Patients must have at least 1A or 2Bs from the following manifestations of SLE, as defined by the BILAG criteria as modified for use in this study, which must be confirmed by the central data reviewer:
 
 a. BILAG A or B score in the mucocutaneous body system b. BILAG A or B score in the musculoskeletal body system due to active polyarthritis as defined in the protocol Section 4.4. 
If only one “B” and no “A” score is present in the mucocutaneous body system or in the musculoskeletal body system due to arthritis, then at least 1 “B” must be present in the other body systems for a total of 2 “B” BILAG body system scores
	
Text updated to clarify that a minimum BILAG 1 ‘A’ or 2 ‘B’ scores is required for screening


PROTOCOL SUMMARY, Statistical Considerations
	
Replace:
 
Baseline and patient characteristics will be summarized via appropriate summary statistics by treatment group and overall, for each phase of the trial.
 
Binary efficacy endpoints will be compared between treatments via Cochran-Mantel-Haenszel (CMH) analysis. Continuous efficacy endpoints will be assessed via analysis of covariance (ANCOVA) repeated measures mixed model analysis with factors including treatment, time, treatment-by-time interaction, baseline covariate, and covariate-by-time interaction. Summary statistics will be provided by dose/treatment for all safety endpoints. Details will be provided in the statistical analysis plan (SAP).
 
Two IAs are planned for this study. The initial IA (IA1) will be conducted at the time of the POC decision for dose selection. The second IA (IA2)
	
The futility analysis was removed due to the modest size of the trial but more importantly because the least reliable data (high placebo response) is known to occur during the first half of the study (before week

Section	Description of Changes	Rationale
	
will be performed for futility. IA2 is planned to be conducted when SRI-4 response is determined for approximately 60 patients (including all patients at the same dose level/matching placebo from the MAD study) after completing 3 months of treatment. The purpose of IA2 is to assess if the trial could stop for an early futility conclusion, or continue. Since there is no plan to stop the trial for an early efficacy conclusion, there is no impact on the type 1 error level.
 
AEs will be summarized by counts and percentages of patients by treatment group. Laboratory data and vital signs will be summarized by treatment group as summary statistics for value and change from baseline at each individual time point. Summary statistics will include n, arithmetic mean, median, arithmetic SD, minimum, and maximum.
 
The PK parameter data will be listed and summarized descriptively in tabular format. Binary PD endpoints will be assessed for the full analysis set (FAS) population via CMH analysis. Continuous PD endpoints will be assessed via ANCOVA repeated measures mixed model analysis with multiple factors. PK and PD relationships will be explored graphically and where appropriate model based methods of analysis will be used.
 
With:
 
Two analyses are planned: 1) an interim analysis to select the Phase 2 dose based on Phase 1 data, and 2) a final analysis at study completion. Additionally, DMC safety analyses will be performed after each Phase 1 cohort and throughout Phase 2 to monitor patient safety.
 
Unless stated otherwise, statistical testing will only be performed on the Phase 2 data and will be done using 2-sided overall alpha of 0.10. Data will be summarized descriptively by treatment and overall for each study phase. For the MAD phase, BOS161721 will be summarized overall and by each dose level and placebo patients from each cohort will be combined.
 
The descriptive summaries for the categorical data will include number and percentage. The descriptive summaries for the continuous data will include number, mean, standard deviations (SD), 25th and 75th percentiles, minimum, median, and maximum. Counts medians, 25th and 75th percentiles, and standard error will be presented for time-to-event data.
 
All safety analyses will be performed using the safety analysis set (SS), defined as all patients who receive at least 1 dose of study treatment. All efficacy analyses will be performed using the full analysis set (FAS), defined as all patients who have receive at least 1 dose of study treatment and have at least 1 evaluable post-baseline efficacy evaluation. Select efficacy analyses may also be performed on the per protocol (PP) set.
 
Binary efficacy endpoints, including the primary efficacy endpoint, will
	
24) when futility analysis was planned
 
Text updated to allow use of testing procedures that are not typical/straight forward as 1-sided (such as CMH).
 
Simplification and consistency with binary endpoints. Allows more


Section	Description of Changes	Rationale																
	
be assessed via Pearson’s chi-squared analysis.
 
Continuous efficacy endpoints will be assessed via analysis of variance (ANOVA) or analysis of covariance (ANCOVA) when applicable, adjusting for the baseline value. Repeated measures mixed models may be performed to evaluate data collected at each visit and overall. Time-to-event endpoints will be assessed via Kaplan-Meier methodology and treatment will be compared using the log-rank test.
 
Adverse event data will be coded to system organ class and preferred term using the Medical Dictionary for Regulatory Activities (MedDRA). The number and percentage of patients experiencing any treatment-emergent AE, overall, and by system organ class and preferred term will be tabulated. Treatment-emergent AEs will also be summarized by severity and relationship.
 
Concomitant medications will be summarized, based on coded terms, using frequency and percentage of patients. Observed values and changes from baseline in vital signs, ECG readings, and hematology and clinical chemistry parameters, will be summarized at each individual visit.
	
flexibility in handling missing data.
																

List of Abbreviations
	
Add:
 
 
 ANOVA	analysis of variance	
 
 ANCOVA	analysis of covariance	
 
 CS	corticosteroids	
 
 CCI	[REDACTED]	
 
 FAS	full analysis set	
 
 MedDRA	Medical Dictionary of Regulatory Activities	
 
 PP	per protocol	
 
 SS	safety analysis set	
 
	ANOVA	analysis of variance	ANCOVA	analysis of covariance	CS	corticosteroids	CCI	[REDACTED]	FAS	full analysis set	MedDRA	Medical Dictionary of Regulatory Activities	PP	per protocol	SS	safety analysis set	
Updated to align with abbreviations added throughout the protocol

ANOVA	analysis of variance																	
ANCOVA	analysis of covariance																	
CS	corticosteroids																	
CCI	[REDACTED]																	
FAS	full analysis set																	
MedDRA	Medical Dictionary of Regulatory Activities																	
PP	per protocol																	
SS	safety analysis set																	

List of Abbreviations
	
Delete:
 
 
 RNP	ribonucleoprotein	
 
	RNP	ribonucleoprotein	
Updated to align with abbreviations deleted throughout the protocol
														
RNP	ribonucleoprotein																	

Section 1.2.3, Study Dose Selection
	
Delete:
 
In addition, the DMC and Boston Pharmaceuticals will conduct a data review for the first interim analysis (IA1). At that time, a decision will be made to suggest which dose should be carried forward into the proof of concept (POC) Phase 2 study.
	
The futility analysis was removed due to the modest size of the trial but more importantly
																

Section	Description of Changes	Rationale
Section 1.2.4, Risk-Benefit Assessment	Replace: Thereafter, DMC monitoring will be conducted periodically throughout the study as described in the DMC charter. With: Thereafter, DMC safety reviews will be conducted periodically throughout the study as described in the DMC charter.	because the least reliable data (high placebo response) is known to occur during the first half of the study (before week 24) when futility analysis was planned Text updated for clarification

Section	Description of Changes	Rationale
Section 2, Study Objectives And Endpoints	Replace: This trial has separate primary and secondary objectives for the MAD Phase 1b and POC Phase 2 studies. With: This trial has separate objectives and endpoints for the MAD Phase 1b and POC Phase 2 studies. The primary, secondary, and exploratory objectives for each phase, as applicable, are described below with their corresponding endpoints.	Text updated to appropriately setup table
Section 2, Study Objectives And Endpoints	The objectives and endpoints sections (Section 2 and 3 in Amendment 1) were combined into 1 section (Section 2 of Amendment 2) and the objectives and endpoints are now in a table format to easily distinguish which endpoints align with each objective. Additional edits were made to the objectives and endpoints. Some new endpoints were added to the study. An exploratory objective, to examine PK and PD effects of BOS161721 in subjects with mild to moderate SLE, was changed to ‘secondary objective’. Changes to the objectives and endpoints are noted below:	Updated for clarity and to provide a comprehensive list of endpoints identified in the protocol

